8. CORRELATIVE/SPECIAL STUDIES

8.1 Pharmacokinetic Studies

Ofatumumab concentrations are determined in EDTA plasma (i.e., one lavender-topped Vacutainer). Samples must be processed in a refrigerated centrifuge (4°C) at 1600g for 15 minutes and frozen at -20°C within 4 hours of collection. The ofatumumab PK samples may be batched at participating sites and/or sent directly to Novartis. The shipping information will be enclosed with the study kits.

Pharmacokinetic sampling for ofatumumab will be as follows:

- Cycle 3 Day 1 – Predose, EOI
- Cycle 3 Day 8 – Predose
- Cycle 3 Day 15 – Predose
- Cycle 4 Day 22 (last weekly Ofatumumab dose) – Predose, EOI
- Cycle 5 Day 1 (first monthly Ofatumumab dose) – Predose, EOI
- Cycle 8 Day 1 (last monthly Ofatumumab dose) – Predose, EOI
- 2 months after Ofatumumab therapy completed – Predose
- 6 months after Ofatumumab therapy completed - Predose

Samples will also be obtained for idelalisib pharmacokinetics. These will be determined in K2 EDTA plasma (i.e., one lavender-topped Vacutainer), obtained pre-dose (trough) and 1.5 hours post-dose (peak) with a +/- 10 minute window for post-dose. After drawing invert the tube at

CONFIDENTIAL

This document is confidential. Do not disclose or use except as authorized.

least 8 to 10 times. Keep sample in wet ice prior to centrifugation. It is preferred the sample be centrifuged within 30 minutes and must be centrifuged within 2 hours of blood collection. Centrifuge at a minimum of 1500 to 2000 x g for 15 minutes until cells and plasma are well separated. Use pipette provided to transfer the plasma equally into four appropriately labeled tubes. Samples will be processed on-site, stored at -70°C, then batched and shipped approximately every 6 months. If your site can only store in a -20 °C freezer, please send the PK sample shipments monthly. The idelalisib PK samples may be batched at participating sites then sent after freezing. Please ship frozen samples on dry ice to Covance Laboratory Inc. at the following address:

Attention: [name]
Bioanalytical Principal Investigator
Sample Management—Bioanalytical (Rm 1S 160)
Covance Laboratory Inc.
[name]
Madison, WI 53704-2523

Pharmacokinetic sampling for idelalisib will be as follows:

Staggered:

- Cycle 1 Day 1
- Cycle 2 Day 1
- Cycle 3 Day 1 (first weekly dose of Ofatumumab)
- Cycle 4 Day 22 (last weekly dose of Ofatumumab)
- Cycle 8 Day 1 (last monthly dose of Ofatumumab)
- 2 and 6 months after end of ofatumumab therapy.

8.2 Pharmacodynamic Studies

8.2.1 Biological Features of the CLLs

FISH will be determined on either peripheral blood or bone marrow for the common CLL probes (17p, 11q, +12, 13q and t(11;14) to rule out mantle cell lymphoma) at the local institutions prior to enrollment, and this report will be supplied to the Coordinating Center at the time of Registration.

IGHV, CD38 and ZAP70 will be determined by the CLL Research Consortium central tissue bank. All participating CLL Research Consortium sites are required to enroll participants on the above tissue bank, using the dedicated consent form for that study at each institution. Patients already enrolled in the CLL Research Consortium central tissue bank need to provide the results of these tests to the Coordinating Center at the time of registration.

At screening for this study three additional sodium heparin green top tubes of peripheral blood will be submitted to the Tissue Bank for banking if a patient is already enrolled in the CLL Research Consortium

CONFIDENTIAL

This document is confidential. Do not disclose or use except as authorized.

If a site is *not* participating in a CLL Research Consortium tissue bank study, the participant will be required to provide three sodium heparin green top tubes of peripheral blood at screening, cycle 3 day 1 and progressive disease or off study due to toxicity. These samples will then be shipped overnight to [name] at the above CRC address in Section 8.1. In the case of closures of the CRC, a temporary covering or local lab may be designated. Guidance will be provided by correspondence in such cases.

In addition, a saliva sample will be collected at screening using Oragene collection device and shipped to:

Dana Farber Cancer Institute
CLL Center, [name] Lab
ATTN: [name]
[name]
[name] (Ref. 13-309)
Boston, MA 02115

CD38 will be determined at screening at the CLL Research Consortium tissue bank.

8.2.2 DFCI Studies: Genomic Profiling

Four 10 cc sodium heparin (green top) tubes of peripheral blood will be drawn at screening, and saliva will be collected using Oragene collection devices. Heparinized bone marrow aspirate (5-10 cc) should be sent in addition.

At the time that patients come off study for toxicity or progressive disease, four 10 cc sodium heparin (green top) tubes of peripheral blood should again be drawn and shipped overnight at ambient as below. If a patient coming off study due to progressive disease or toxicity is undergoing a bone marrow biopsy, and in particular if they do not have significant circulating disease, please also send heparinized bone marrow aspirate (5-10 cc).

These samples will then be shipped overnight to [name] at the above CRC address in Section 8.1.

From the blood samples, PBMCs or CLL B-cells will be isolated and viably frozen, for subsequent use in SNP array, gene expression, miRNA profiling and whole exome sequencing. Saliva will be isolated and stored according to the kit directions until DNA is prepared.

8.2.3 DFCI Studies: Elucidation of subclonal architecture of CLL treated with idelalisib

The goal of this correlative study is to elucidate the dynamics of CLL subclones during therapy with idelalisib, in particular by comparing blood and bone marrow prior to therapy and after two months of single agent idelalisib. We will also look at the acute alteration in the subclonal architecture in blood after several weeks of idelalisib, in order to explore the effect of redistribution lymphocytosis on the clones present in blood. We will then compare these results

CONFIDENTIAL

This document is confidential. Do not disclose or use except as authorized.

to the features of persistent subclones present in blood and bone marrow at time of final restaging. Eventually, at time of relapse, samples will be banked for comparison to the earlier data on clonal architecture, in order to identify the subclone that has led to relapse and to place it in context of the prior data. We expect that these data will greatly enhance our understanding of the relationship of CLL cells in blood and bone marrow and how that changes with idelalisib therapy, as well as giving us critical information on both primary and acquired resistance to idelalisib.

Experimental Procedures: We propose to perform serial exome sequencing (WES) on a selection of patients from this trial, selected to represent the range of CLL prognostic factors and a range of initial idelalisib responses. We will include roughly half *IGHV* mutated and unmutated patients, and half those who had stable disease (SD) after 2 months of single agent idelalisib vs those with partial response (PR) or partial response with lymphocytosis (PRL) after two months of therapy. Relatively few patients on this study have high risk del 11q or del 17p cytogenetics but we will prioritize those patients for analysis (n=3). The plan will be to perform WES on baseline blood, bone marrow and germline (saliva) samples, on blood and bone marrow from end of single agent cycle 2 restaging, and on blood and bone marrow from final restaging at cycle 10. These samples will allow determination of the relative distribution of clones in blood and bone marrow at the same timepoint, how this is altered by idelalisib, and ultimately which clone(s) persist at the time of low level residual disease. In addition we will sequence peripheral blood at one additional timepoint, week 2-4 on single agent idelalisib, with the goal of assessing the alteration of clonal architecture of CLL in the blood during idelalisib-mediated redistribution. We will study 8 samples for each of 10-15 patients initially, and then follow these patients serially over time and bank them again at relapse, at which time we will sequence them again, for comparison to the initial and residual disease subclones. These studies will continue as sufficient samples have already been banked.

8.2.4 Flow cytometry for activation markers, adhesion molecules and CD20 levels

Flow cytometry analysis for cell surface adhesion molecules and activation markers including CXCR4, CXCR5, PD-1, PD-1L, CD38, CD40, CD80, CD86, CD154 and Ki67 will be performed. T cell subsets and immunomodulatory effects on T cells may also be analyzed on these samples. Plasma will be collected for analysis of cytokine levels including CCL3 and CCL4 at the same timepoints.

At the following time points, collect two 10cc sodium heparin green top tubes:

Screening

Cycle 1 Day 8

Cycle 1 Day 15

Cycle 2 Day 1

Cycle 2 Day 22 (two month restaging)

Cycle 3 Day 8

Cycle 3 Day 15

Cycle 4 Day 22

Cycle 10 Day 1 (final restaging)

CONFIDENTIAL

This document is confidential. Do not disclose or use except as authorized.

In addition, the same markers will be assessed on bone marrow aspirates (5-10cc) at the following time points:

Screening

Cycle 2 Day 22 (two month restaging)

Cycle 10 Day 1 (final restaging)

All samples should be sent to [name] at the CLL Research Consortium address above in Section 8.1.

8.2.7 Mayo Clinic Microvesicle Studies

CONFIDENTIAL

This document is confidential. Do not disclose or use except as authorized.

For these studies, a 10 cc sodium heparin green top tube and bone marrow aspirate (a couple ccs if a bone marrow is being performed otherwise) will be drawn at screening (only marrow at screening), cycle 2 day 22(end of single agent idelalisib therapy), cycle 10 day 1(final restaging), every 6 months for the first year in follow-up (if a bone marrow is being performed for clinical reasons) and when a patient comes off study due to progressive disease or toxicity. These samples will be shipped overnight ambient to [name] at the above address. On arrival they will be spun in a 15 cc conical tube 3 x 2500g for 20 min at room temperature, and the platelet-free plasma will be carefully decanted into a fresh tube without disturbing the pellet. They can then be aliquoted in 1 ml aliquots in eppendorf tubes and frozen at -80C.

9. STUDY CALENDAR

Screening evaluations are to be conducted within 14 days prior to start of protocol therapy. Scans and Bone Marrow Biopsies must be done ≤ 4 weeks prior to the start of therapy. In the event that the participant's condition is deteriorating, laboratory evaluations should be repeated within 48 hours prior to initiation of the next cycle of therapy.

All assessments must be performed prior to administration of any study medication. All study assessments and medications should be administered within ± 3 days of the protocol-specified date during the induction phase and ± 7 days of the protocol-specified date in the post-induction phase, unless otherwise noted.

Table 10

Procedures	Screen	Treatment Phase					Post Induction Phase		Long Term Follow-up	Survival Follow-up
		Cycle 1-2 Idelalisib only (Days 1-56)	Cycle 3 & 4 Weekly Ofa + Idelalisib ¹⁵	Cycle 5-8 Monthly Ofa + Idelalisib	Restage Cycle 4 day 22	Cycle 2 day 22 (Restage end of cycle 2), Cycle 10 day 1 (Final Restage 2 months after end of ofa therapy) and off treatment prior to cycle 10	Cycle 9 Day 1	Every 2 mos while on study drug beginning Cycle 10		
								Every 3 or 6 months ¹¹	Yearly	

CONFIDENTIAL

This document is confidential. Do not disclose or use except as authorized.

Informed Consent	X									
Demography	X									
Medical History	X									
Bone marrow biopsy	X ¹					X ¹		X ¹		
Flow Cytometry by Marrow or blood ¹⁶	X				X	X				
MRD on bone marrow						X				
CT (Chest Abdomen Pelvis)	X ²				X ²	X ²		X ²	X ²	
Tumor Assessment by PE	X				X	X	X	X	X	
CLL FISH panel (on bone marrow)	X					X (ON BONE MARROW)				
Banking at CRC, with Flow Cytometry ³	X	C1 DAY 8 & 15, C2 DAY 1	C3 D8 & 15, C4 D22			X				
DFCI Studies: Genomic Profiling ⁴	X							End of therapy ⁴		
Banking at Clinical Research Consortium for Sites participating in a CRC study ¹⁷	X									
Procedures	Screen	Treatment Phase					Post Induction Phase		Long Term Follow-up	Survival Follow-up
		Cycle 1-2 Idelalisib only (Days 1-56)	Cycle 3 & 4 Weekly Ofa + Idelalisib ¹⁵	Cycle 5-8 Monthly Ofa + Idelalisib	Restage Cycle 4 day 22	Cycle 2 day 22 (Restage end of cycle 2), Cycle 10 day 1 (Final Restage 2 months after end of ofa therapy) and off treatment prior to cycle 10	Cycle 9 Day 1	Every 2 mos while on study drug beginning Cycle 10	Every 3 or 6 months ¹¹	Yearly

CONFIDENTIAL

This document is confidential. Do not disclose or use except as authorized.

Banking at Clinical Research Consortium for Sites not participating in a CRC study ¹⁸	X		C 3 D1						X	
PK samples, ofatumumab ⁵			C3 D1, 8, 15; C4 D 22	CYCLE 5 D 1 & CYCLE 8 D 1		FINAL ONLY		6 MOS		
PK samples, idelalisib ⁵		DAY 1 EACH CYCLE	CYCLE 3 DAY 1, CYCLE 4 DAY 22	CYCLE 8 DAY 1		FINAL ONLY		6 MOS		
OSU Studies ⁶	X	CYCLE 1 DAY 1, 15; CYCLE 2 DAY 1	CYCLE 3 DAY 1			TWO MONTH ONLY				
Mayo Studies ⁷	X		CYCLE 3 DAY 1			FINAL ONLY			EVERY 6 MONTHS FOR FIRST YEAR; & AT PD	
Physical Exam	X	WEEKLY	CYCLE 3 DAY 1, 8, 15, CYCLE 4 DAY 1, 15	MONTHLY	X	X	X	X	X	
ECOG	X	WEEKLY	WITH PE	WITH PE	X	X	X	X		
Height	X						X			
Weight	X		X	X	X	X	X	X		
Vital Signs ¹²	X	WEEKLY	WEEKLY	MONTHLY	X	X	X	X	X	
12-lead ECG	X									
Procedures	Screen	Treatment Phase					Post Induction Phase		Long Term Follow-up	Survival Follow-up
		Cycle 1-2 Idelalisib only (Days 1-56)	Cycle 3 & 4 Weekly Ofa + Idelalisib ¹⁵	Cycle 5-8 Monthly Ofa + Idelalisib	Restage Cycle 4 day 22	Cycle 2 day 22 (Restage end of cycle 2), Cycle 10 day 1 (Final Restage 2 months after end of ofa therapy) and off treatment prior to cycle 10	Cycle 9 Day 1	Every 2 mos while on study drug beginning Cycle 10	Every 3 or 6 months ¹¹	Yearly

CONFIDENTIAL

This document is confidential. Do not disclose or use except as authorized.

Adverse Events	X	WEEKLY	WITH PE	WITH PE	X	X	X	X	X ⁸	
Concomitant Therapy	X	WEEKLY	WITH PE	WITH PE	X	X	X	X		
Chemistry ¹³	X	WEEKLY ¹³	WEEKLY THROUGH H C4 D 22 ¹³	MONTHLY	X	X	X	X	X	
Hematology ¹⁴	X	WEEKLY	WEEKLY THROUGH H C4 D 22	MONTHLY	X	X	X	X	X	
Beta-2-microglobulin	X				X	X		EVERY 6 MOS	EVERY 6 MOS	
Immunoglobulins (IgG, IgM, IgA)	X				X	X		EVERY 6 MOS	EVERY 6 MOS	
Serum protein electrophoresis	X				X	X		EVERY 6 MOS	EVERY 6 MOS	
CD4 count	X				X	X		EVERY 6 MOS	EVERY 6 MOS	
Direct Coombs test	X									
Serum Pregnancy Test ⁹	X		MONTHLY	X		X		ONCE 5 MONTHS POST OFA		
Hepatitis B surface antigen and antibody ¹⁰ , Hepatitis C antibody, HIV	X									
Survival follow-up by telephone or clinic visit note										X

1. Bone marrow biopsies are required at screening, cycle 2 day 22 (end of cycle 2 restaging) and cycle 10 day 1 (final restaging). Those patients in clinical CR at any bone marrow restaging should have 4 color MRD flow cytometry performed at the time of their bone marrow evaluation. Bone marrow biopsy can also be done at any subsequent point to confirm a suspected CR. In addition to standard clinical testing, 15 cc bone marrow aspirate will be obtained at each bone marrow biopsy, for flow cytometry immunophenotyping and comparison to PB, as well as studies at OSU and Mayo Clinic. These heparinized aspirate samples will be sent to the CRC for processing and storage. In cases where it is unsafe or not feasible to obtain the appropriate quantity of aspirate, the performing clinician should indicate this in his/her note.
2. CT scan required at screening, cycle 2 day 22 (end of cycle 2), cycle 4 day 22, and cycle 10 day 1 (final restaging). In subsequent follow-up only if clinically indicated at investigator discretion and when a patient comes off treatment due to disease progression or toxicity. A CT scan of the chest, abdomen, pelvis and any other known sites of disease should be completed. Any regions captured at screening such as the neck must be followed by CT throughout subject's participation. All CT scans will be centrally reviewed. These scans should be burned onto CD and sent via FedEx to the Project Manager at DFCI, ATTN: (Project Manager), [name], Boston, MA 02215. The scan will then be reviewed at the Tumor Imaging Metrics Core at DFCI.

CONFIDENTIAL

This document is confidential. Do not disclose or use except as authorized.

3. Two sodium heparinized tubes (green tops) at screening and at subsequent times. Sodium heparinized bone marrow aspirate (5-10 cc, green top) at screening and cycle 2 day 22 (end of cycle 2 restaging) and cycle 10 day 1 (final restaging).
 4. Four sodium heparinized tubes (green tops) and saliva. Sodium heparinized bone marrow aspirate (5-10 cc, green top). Patients who come off treatment for toxicity or progressive disease, four 10 cc sodium heparin (green top) tubes of peripheral blood. If a patient coming off treatment due to progressive disease or toxicity is undergoing a bone marrow biopsy, and does not have significant circulating disease, send sodium heparinized bone marrow aspirate (5-10 cc, green top)
 5. For ofatumumab, 2 lavender top tubes. Predose and end of infusion on cycle 3 day 1, cycle 3 day 8, cycle 3 day 15 and cycle 4 day 22 (end of weekly ofa), and cycles 5 and 8 day 1. Note: Predose only for cycle 3 days 8 and 15; and 2 and 6 mos post therapy, no end of infusion.
- For idelalisib, one lavender top predose and one lavender top 1.5 hours post-dose, on Cycles 1-3 Day 1, Cycle 4 Day 22, Cycle 8 Day 1 (last monthly dose of Ofatumumab) and 2 and 6 months after end of ofatumumab.
6. OSU: 3 ACD (yellow top) tubes, 8.5 cc each, + one sodium heparin (green top) tube at screen; 5 ACDs and one heparin on day 1 prior to therapy, 2 ACDs on cycle 1 day 15, 5 ACDs and one heparin on cycle 2 day 1, 3 ACDs and 1 sodium heparin (green top) tube at two month restage, and 2 ACDs on cycle 3 day 1.
 7. Mayo Clinic: 1 sodium heparinized (10 cc green top) tube. Bone marrow aspirate (a couple ccs) will be obtained at each timepoint. At screening only aspirate should be collected.
 8. SAEs and deaths for six months after completion of all therapy.
 9. Only in women of childbearing potential
 10. For those patients who are hepatitis B core antibody positive but surface antigen and HBV DNA negative, monitoring of HBV DNA or viral load is required during the on treatment period at least every 2 months and during follow-up at a minimum of every 2-3 months up to 12 months after the last dose. This testing is also required in the event of development of grade 1 or more elevation in LFTs.
 11. Subjects who discontinue therapy due to an adverse event, but have demonstrated a response of SD or better will enter the follow-up period and be followed every 3 or 6 months until documented relapse or PD, initiation of a new therapy, or for a total of 12 months of follow-up, whichever occurs first.
 12. Vitals Signs include: heart rate, respiratory rate, temperature, blood pressure and oxygen saturation.
 13. Chemistry: Electrolytes, BUN, creatinine, glucose, LDH, phosphate, uric acid, LFTs (total bilirubin, AST, ALT, alkaline phosphatase). Beginning C1D15 through C4D28 a comprehensive metabolic panel (electrolytes, BUN, creatinine, glucose, LDH, phosphate, uric acid, LFTs (total bilirubin, AST, ALT, alkaline phosphatase) will be obtained twice per week. If grade 1 or higher AST, ALT, or bilirubin elevations are noted please see Section 6.2 "Management of Hepatic AEs."
 14. Hematology: CBC, manual differential
 15. Weekly Ofatumumab proceeds through Cycle 4 Day 22.
 16. Flow Cytometry should assess at minimum the following markers: CD5+CD19+, CD19+, CD 20+, CD19+CD23+, CD19+CD38+, kappa and lambda surface immunoglobulins.

Footnotes 16 & 17 outline the sample collection for sites that are or are not participating in the CLL Research Consortium tissue bank study, (for more information-Section 8.2.1):

17. Sites participating in a CLL Research Consortium tissue bank study (Section 8.2.1) provide 3 sodium heparinized (green top) tubes of peripheral blood at screening.
18. Sites *not* participating in a CLL Research Consortium (CRC) tissue bank study (Section 8.2.1) provide 3 sodium heparinized (green top) tubes of peripheral blood at screening, cycle 3 day 1 and coming off study due to disease progression or toxicity. In addition, collect a saliva sample at screening.

Off-Treatment Evaluations

If at all possible, patients going off study should have: hematology, chemistry, beta-2-microglobulin, CD4 count, IgG, IgM, IgA, serum protein electrophoresis, full tumor assessment by CT, bone marrow biopsy and samples for correlative studies. Please obtain the following samples described under genomic and Mayo Microvesicle for correlative studies. If prior to cycle 2 day 22 please obtain any additional studies required for that visit.

CONFIDENTIAL

This document is confidential. Do not disclose or use except as authorized.

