5.5 Duration of Follow Up

Once participants have completed study treatment they will be followed until initiation of new therapy following removal from study, or until death, whichever occurs first. They will be seen every 3 or 6 months in the follow up phase; this will be decided by their treating physician. Follow up will continue for up to 10 years. Participants removed from study for unacceptable adverse events will be followed until resolution or stabilization of the adverse event, and/or until initiation of new therapy for their disease, whichever is longer.

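### Table 10 footnote 7 asks for a Mayo marrow aspirate at every timepoint, while Section 8.2.7 takes one only when a marrow is already being done

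*Combined protocol and SAP*

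**What the plan says.** **Section 8.2.7 (Mayo Clinic Microvesicle Studies)** asks for a blood tube and "bone marrow aspirate (a couple ccs if a bone marrow is being performed otherwise". It lists screening, cycle 2 day 22, cycle 10 day 1, follow-up, and coming off study for progression or toxicity. The follow-up timepoint carries its own condition: "every 6 months for the first year in follow-up (if a bone marrow is being performed for clinical reasons".

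**Section 9, Table 10, Mayo row** has entries at screening, cycle 3 day 1, the final restaging only, and long-term follow-up. The last of these reads "EVERY 6 MONTHS FOR FIRST YEAR; & AT PD", with no condition.

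**Footnote 7**, attached to that row, says "Bone marrow aspirate (a couple ccs) will be obtained at each timepoint". Its only qualifier is that no blood is taken at screening.

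**Footnote 1** sets the marrow schedule: "Bone marrow biopsies are required at screening, cycle 2 day 22 (end of cycle 2 restaging) and cycle 10 day 1 (final restaging". Later marrows are optional, to confirm a suspected complete response. It also says "15 cc bone marrow aspirate will be obtained at each bone marrow biopsy" and names the Mayo work among the uses of that aspirate. The bone marrow row has no entry under Cycles 3 and 4 or under Long Term Follow-up.

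**The concern.** The condition in Section 8.2.7 is what keeps the Mayo marrow from becoming a procedure done purely for research. The calendar, which sites use to schedule visits, leaves it out. A site following footnote 7 as written could perform a marrow aspirate in follow-up with no clinical reason. A site following Section 8.2.7 could appear to have missed samples that the calendar requires. Appendix D, Section 3.9, asks for all departures from defined procedures to be reported, so either site could look non-compliant with the other section.

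The instruction is still in force. Enrolment is closed and idelalisib has stopped, but the rationale for the 3/14/16 amendment (Section 2.5) keeps patients in per-protocol follow-up until further therapy, and Section 1.1 says that correlative analyses continue.

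What is at stake is participant burden and clean sample records in an exploratory correlative study.

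**Working it through.** The plan gives no figure to reproduce. The check sets the texts side by side and then counts timepoints.

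**Step 1: compare the marrow rules by timepoint.**

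| Timepoint | Section 8.2.7 | Mayo row with footnote 7 | Marrow required by footnote 1? |
|---|---|---|---|
| Screening | Yes | Yes | Yes |
| Cycle 2 day 22 | Yes | Not listed (restaging entry is final only) | Yes |
| Cycle 3 day 1 | Not listed | Yes | No |
| Cycle 10 day 1 | Yes | Yes | Yes |
| Follow-up, six-monthly, first year | Only with a clinical marrow | Yes, no condition | No |
| Progression | Only if a marrow is done anyway | Yes | No, but the Off-Treatment Evaluations ask for one if possible |

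The instructions diverge at two places: first-year follow-up and cycle 3 day 1.

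**Step 2: count the follow-up aspirates.** Section 5.5 says "They will be seen every 3 or 6 months in the follow up phase", at the treating physician's choice.

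- Three-monthly visits in year one: months 3, 6, 9, 12.
- Six-monthly visits in year one: months 6, 12.
- If the six-monthly entry means months 6 and 12, both are visits on either schedule, giving 2 Mayo timepoints.
- Marrows scheduled in the Long Term Follow-up column: 0.

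Research-only aspirates per patient under a literal footnote 7, before subtracting any clinical marrow:

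- follow-up ends before month 6: 0
- follow-up ends between months 6 and 12: 1
- patient reaches month 12: 2

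Each timepoint at which a marrow is done for clinical reasons reduces the count by one, because that aspirate is no longer research-only. Under Section 8.2.7 the count is 0 throughout.

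**Step 3: examine cycle 3 day 1.** With 28-day cycles, cycle 2 day 22 is study day 28 + 22 = 50, and cycle 3 day 1 is day 57, which is 57 − 50 = 7 days later. Section 8.2.7 describes its cycle 2 day 22 sample as the end of single-agent idelalisib, and a marrow is required that day. Section 8.2.7 has no cycle 3 day 1 sample, and the Mayo row has no cycle 2 day 22 sample. The simplest explanation is one sample placed under the wrong visit, so it is not counted as an extra aspirate.

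**Step 4: leave out the progression sample.** The Off-Treatment Evaluations already ask, where possible, for a marrow and for the Mayo samples, so footnote 7 adds no separate procedure there.

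**Step 5: check whether the calendar states such conditions elsewhere.** It does. For the genomic samples, footnote 4 limits the off-treatment marrow with "If a patient coming off treatment due to progressive disease or toxicity is undergoing a bone marrow biopsy" and a further condition on circulating disease. Footnote 2 restricts later CT scans in follow-up to clinical indication, apart from those on coming off treatment. Footnote 7 has no comparable clause.

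**The case against.** The strongest reply is that the documents already show which rule is meant. Footnote 1 governs marrow procedures, requires only three, and supplies the Mayo study from aspirate taken at each biopsy. The marrow row is blank in long-term follow-up. Footnotes 3 to 7 mainly list tubes and volumes, so a couple of cubic centimetres reads naturally as an aliquot of a marrow already under way. A site would have to overlook the marrow row, footnote 1 and Section 8.2.7 together to schedule a research-only procedure.

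Most of this stands. Section 8.2.7 is very probably the intended rule, and this is an inconsistency between a section and its calendar, not a disputed design choice. But none of those texts amends footnote 7, which is worded as an instruction. The nursing page sends staff to both Sections 8 and 9 without saying which prevails.

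Two further points also stand. The documents do not name months 6 and 12. And a condition placed in the Mayo follow-up cell would reach the blood tube as well as the marrow, although Section 8.2.7 leaves unclear whether its follow-up condition covers both. The fix should therefore avoid that cell.

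A reader might infer that cycle 3 day 1 adds another research marrow. Step 3 shows why that is unlikely. In any case it could affect only patients who had not reached day 57, and the documents do not show that there were any.

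**Conclusion.** The inconsistency is real and minor. If footnote 7 is followed as written, it asks for up to about two research-only aspirates per patient in the first follow-up year, against none under Section 8.2.7. That ceiling assumes that the six-monthly entry means months 6 and 12, that the patient stays in follow-up to month 12, and that no clinical marrow coincides.

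A reader might multiply two by the 27 enrolled patients to get a trial total. The documents do not support that: they do not say how many patients reach each timepoint or have clinical marrows. A reader might also infer that unnecessary aspirates have been done, and nothing in the documents shows this.

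The overall response rate, its confidence interval and the listed secondary analyses are unaffected. Confidence is high in the textual mismatch and lower in any practical burden, which depends on how sites read the calendar.

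**What to change.** Make two edits to Section 9.

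1. **Footnote 7, aspirate sentence only.** State that the aspirate is taken only when a bone marrow is already being performed (in follow-up, only for clinical reasons), per Section 8.2.7. Leave the blood-tube sentence and the follow-up cell unchanged, so that no blood sample is cancelled by accident.
2. **Mayo row.** Move the cycle 3 day 1 entry to cycle 2 day 22, so that the restaging entry covers cycle 2 day 22 and the final restaging. This matches Section 8.2.7 and uses a marrow already required. The two edits belong together: with footnote 7 made conditional and the entry left at cycle 3 day 1, where no marrow is scheduled, the calendar would lose the end-of-single-agent Mayo marrow.

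The cost is one clause and one moved table entry. Section 13.1 requires protocol changes to go to the IRB as amendments, so both could be included in the next one. Neither adds a procedure or changes an endpoint or analysis.
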